3.1.3 Dose De-escalation

Up to six subjects will initially be treated with pomalidomide at dose level 1, 5mg PO daily for 21 days followed by 7 days 'rest' to complete the 28 day cycle. Subject to toxicity evaluation (Section **3.1.2**), this dosage may be deescalated to dose level minus 1, 3mg PO daily for 21 days followed by 7 days 'rest' to complete the 28 day cycle in a second cohort of up to six subjects.

A dose will be considered as toxic if two or more of the subjects entered at that dose level develop a DLT within the first 8 weeks (2 cycles) of drug administration. This time period has been selected, in line with prior HAMB studies, as in the great majority of cases KS will require

at least 8 weeks of treatment. The tolerated dose will be defined as the highest dose level administered as part of the protocol where 0 or 1 of 6 subjects experience a dose limiting toxicity within the first 8 weeks of drug administration.

If it is determined that a dose is toxic then subjects in that group who have not experienced a DLT or off-therapy criterion will be dropped to the next lower level. In the case that the lowest predetermined dose is determined to be toxic, all subjects will cease therapy unless in the interim the protocol has been amended by seeking IRB approval to include an additional lower dose level.

3.1.4 Antitumor Activity Assessment

If either dose proves tolerable, additional subjects will be added at the highest tolerable dose to gain preliminary information on activity, to a goal of 15 HIV positive and 10 HIV negative subjects evaluable for response. Only subjects who complete at least two cycles of therapy will be considered evaluable for response. For subjects in the anti-tumor activity assessment phase whose KS is HIV-associated, more stringent entry criteria will apply to be considered evaluable for response (Section 2.1.1.15); all subjects with non-HIV-associated KS who complete at least two cycles of therapy will be considered evaluable for response.

In the absence of off-therapy criteria, therapy will continue for 24 weeks (6 cycles of 4 weeks each). Subjects who, in the opinion of the investigators, are continuing to derive benefit may continue on therapy for up to an additional 24 weeks (6 additional cycles). Examples of derived benefit to be used in consideration of possible additional therapy include, but are not limited to, the following:

- 3.1.4.1 Achievement of partial response from baseline (Section 6.2) with evidence of continuing disease improvement on therapy
- 3.1.4.2 Achievement of stable disease (Section 6.2) in subjects whose disease was progressing at baseline
- 3.1.4.3 Improvement in tumor-associated edema or pain (objective as measured by limb circumference, or subjective as measured by analgesia or diuretic requirements)
- 3.1.4.4 Improvement in quality of life measures, such as KS-associated impairment of activity or mobility or social withdrawal.

Up to two subjects at each dose level who are removed from study prior to the completion of 8 weeks of therapy for reasons other than drug toxicity, whether in the dose establishment phase or antitumor activity assessment phase, may be replaced at the discretion of the Principal Investigator or Lead Associate Investigator.

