6.2 RESPONSE CRITERIA

While the evaluation of the response of KS to an agent or regimen is difficult to grade by means of commonly used oncologic definitions, in an effort to standardize the evaluation of therapy against KS, the AIDS Clinical Trial Group Oncology Committee has devised a set of staging and response definitions for KS. We will use a modification of these criteria to assess responses, which is consistent with the criteria used in our previous KS studies. It should be noted that there is some observer variability in the evaluation of the number, size, nodularity, and color of lesions, and this must be taken into account when measurements are interpreted.

- For the purposes of this study, patients should be evaluated at baseline and re-evaluated for response on day 1 of every cycle or every other cycle depending on study (see sections [6.2.1](#) and [6.2.2](#) below) and at the end of treatment.
- For assessment of response, only patients who complete at least two cycles of therapy are evaluable.
- For evaluation of less than complete responses in subjects with more than 50 lesions at entry, only the previously selected 1 - 3 representative areas that contain at least 20 lesions will be considered. However, complete responses still require the absence of any detectable disease over the entire body (i.e. not confined to the representative areas).

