10.4 STATISTICAL ANALYSES

An initial toxicity assessment phase of the trial will be conducted in which up to six subjects will be treated with pomalidomide at 5mg daily for 21 days of a 28 day cycle. If two or more subjects experience a DLT within the first two cycles (eight weeks), then up to six subsequent subjects will be treated at 3 mg daily for 21 days of a 28 day cycle. The highest dose at which zero or one of six subjects experience a DLT during the first two cycles (eight weeks) will be used to determine potential clinical activity.

Once the dose for assessment of clinical activity is determined, two expansion cohorts will be established to investigate response rate. These will be established with the goal of enrolling ten evaluable HIV negative patients, and fifteen evaluable HIV positive patients. Where KS is HIV-associated, these latter subjects will have somewhat more stringent entry criteria with respect to KS not responding to HAART to enable a better assessment of any anti-tumor activity uncomplicated by tumor responses associated with HAART initiation (inclusion criterion **2.1.1.15** above). Subjects treated at the dose chosen for assessment during the toxicity

assessment phase who met these additional eligibility criteria at study entry will be considered evaluable for response for this part of the study, in the appropriate cohort.

There are two circumstances under which an individual subject's dose could be de-escalated: first if two other subjects on the same dose level experience a DLT (Section 3.1.3), and second if the subject experiences a non-thromboembolic DLT on the higher dose level which resolves within 28 days (Section 3.3). In either instance, if the subject is evaluable they will be considered part of the initial (higher) dose cohort for the purposes of evaluating response.

At the dose for assessment of clinical activity, two cohorts of patients will be evaluated according to their HIV status as follows:

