Of the ten evaluable subjects enrolled in the HIV negative expansion cohort, the probability of three or more responding (complete responders plus partial responders) is 83.3% if the true probability of a response is 40%, and 7.0% if the true probability of a response is 10%. Thus, obtaining at least three subjects with a response in the ten HIV negative evaluable subjects is more likely to be consistent with a $\geq 40\%$ true response rate than with a $\leq 10\%$ true response rate. This outcome (three or more responders) will be considered sufficiently positive for further investigation of the agent in this group.

Of the fifteen evaluable subjects enrolled in the HIV positive expansion cohort, the probability of four or more responding (complete responders plus partial responders) is 90.9% if the true probability of a response is 40%, and 5.6% if the true probability of a response is 10%. Thus, obtaining at least four subjects with a response in the 15 evaluable HIV positive subjects is more likely to be consistent with a $\geq 40\%$ true response rate than with a $\leq 10\%$ true response rate. This outcome (four or more responders) will be considered sufficiently positive for further investigation of the agent in this group. As of the submission of amendment G, fifteen evaluable subjects in the HIV positive expansion cohort have been accrued to address the primary question of assessing the anti-tumor effect of pomalidomide in those patients. The responses for these 15 subjects will be reported together with the 7 subjects enrolled to date in the HIV negative expansion cohort. The protocol allows for accrual up to 18 HIV (+) patients and 10 HIV (-) patients. As the endpoint for activity has been reached for the HIV (+) patients at this time, the initial analysis describing the activity of pomalidomide in KS will include only patients entered up until this time. Any additional subjects accrued after this point in either cohort (up to 3 in each cohort) will be primarily evaluated for correlative endpoints; they will also be included in any description of long term clinical outcomes at a later point.

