At the conclusion of the trial, the response rates from the two cohorts will be compared and if they are sufficiently similar ($p > 0.30$ by a two-tailed Fisher's exact test), in addition to being reported separately, they can be pooled together and also reported in that manner. Also, after the all patients have been evaluated for response, 95% confidence intervals will be formed about the response rate in both cohorts, as well as together, if sufficiently similar. The maximum confidence interval widths would be $\pm 32\%$ with 10 patients, $\pm 26\%$ with 15 patients, and $\pm 20\%$ with 25 patients.

To allow for the possibility of different accrual rates between these two cohorts in this rare disease, up to an additional three subjects may be accrued to the evaluable HIV positive cohort (for a maximum of eighteen) in the case that ten evaluable HIV negative subjects have not yet been accrued at the time that accrual of evaluable HIV positive subjects reaches fifteen. In the

event that 16 to 18 HIV positive patients are enrolled, 4 or more responders will still be needed to be considered sufficiently positive for further investigation.

Response rates will be estimated for pomalidomide. Survival analysis will be performed using Kaplan-Meier methods. Progression-free survival will be defined as the time from Day 1 of a given intervention until progression *requiring a change in therapy*. Event-free survival will be defined as the time from Day 1 of a given intervention until progression *requiring a change in therapy* or death as a result of any cause. All results will be carefully reported in the context of the limited size of the study.

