For those subjects who obtain a clinical complete or partial response or clinical benefit from initial treatment with pomalidomide, and subsequently again manifest KS requiring therapy while not receiving pomalidomide, an additional course of treatment with pomalidomide may be offered as described in Section 3.1.6. Based on responses seen at the time of this amendment (January 2013) and our experience with treatment of KS, it is anticipated that approximately 3-6 subjects will potentially be eligible for and receive an additional course of therapy, but this estimate will be refined as further subjects are enrolled and become assessable for response. The scientific objective of this cohort will be to explore the safety and tolerability of a second course of pomalidomide in patients who had previously benefited from the agent: this exploration will comprise a secondary objective for the protocol overall. As a further objective, tumor response rates in this cohort will also be evaluated with exploratory intent; and virologic and immunologic correlative studies will be performed for comparison with those obtained during the first treatment course. For those subjects treated with this additional course, a new tumor baseline will be taken, and the subsequent response to treatment from this baseline will be determined. The fraction of the patients who receive the extra course who respond to treatment (complete responders plus partial responders) will be determined and estimated along with a 95% confidence interval. The results obtained following this subsequent treatment will be presented separately from those for the initial treatment.

Each of the correlative analyses will be evaluated with exploratory intent, using non-parametric methods generally, and without formal adjustment for multiple tests performed. Results will be presented in the context of a hypothesis generating study.

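### First-course response is planned only in subjects who finish two cycles; without an all-treated rate beside it, the reported rate will tend to overstate response among those treated

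*Combined protocol and SAP*

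**What the plan says.** The restriction appears twice. Section 3.1.4 has "Only subjects who complete at least two cycles of therapy will be considered evaluable for response", and section 6.2 has "For assessment of response, only patients who complete at least two cycles of therapy are evaluable".

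Section 10.4 builds on that set. The targets are 15 HIV positive and 10 HIV negative evaluable subjects, and the operating characteristics are stated for them, for example "Of the fifteen evaluable subjects enrolled in the HIV positive expansion cohort, the probability of four or more responding". For estimation, "95% confidence intervals will be formed about the response rate in both cohorts", with a pooled rate if the cohorts look alike. No other first-course denominator is named.

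Three neighbouring rules do not fill the gap:

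- **Dose reduction (10.4).** "In either instance, if the subject is evaluable they will be considered part of the initial (higher) dose cohort". The condition of being evaluable remains, so early leavers do not come back in.
- **Replacement (3.1.4).** Up to two subjects per dose level who leave before 8 weeks for reasons other than drug toxicity may be replaced. Nothing says the replaced subject still counts for response.
- **Report at amendment G (10.4).** "The responses for these 15 subjects will be reported together with the 7 subjects enrolled to date in the HIV negative expansion cohort". The 15 are described as evaluable and the 7 as enrolled, so it is unclear whether both counts follow one definition.

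**The concern.** Whether a subject finishes two cycles is known only after dosing has begun. Section 3.6.1 allows therapy to end earlier for grade 4 dose-limiting toxicity, thrombosis, poor performance status, non-adherence, the subject's own request or investigator discretion. Several of these are treatment failures, yet each takes the subject out of the response denominator.

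The expected direction follows from the endpoint. Section 6.2.3 requires a response to last at least four weeks, and section 6.2.1.2 schedules marker-lesion records on day 1 of each cycle. Leavers will therefore seldom be responders, and leaving them out raises the rate.

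At stake is how the activity result is read. Section 1.1.2 lists antitumor effect as a preliminary secondary objective, but section 10.4 calls it the primary question for the HIV positive cohort and ties a decision on further investigation to it. A reader given only the evaluable rate cannot tell whether the selection effect was nil or several points.

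**Working it through.** **1. The plan's own figures.** Exact binomial tails for evaluable subjects:

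| Rule | True rate 40% | True rate 10% |
|---|---|---|
| at least 3 of 10 | 0.8327 (stated 83.3%) | 0.0702 (stated 7.0%) |
| at least 4 of 15 | 0.9095 (stated 90.9%) | 0.0556 (stated 5.6%) |

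All four reproduce. They describe the evaluable rate only.

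**2. Why leavers are rarely responders.** After baseline, lesions are recorded on cycle 2 day 1 (study day 29) and cycle 3 day 1 (study day 57), 28 days apart. Two cycles last 56 days. Scheduled on-treatment visits therefore cannot confirm a four-week response before two cycles are complete. The exceptions are a subject who stops during cycle 2 and is confirmed at the final-cycle day 29 or a later visit (3.4.5), or one who stops for confirmed complete remission (3.6.1.5). Both should be rare.

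**3. Size of the bias.** Let d be the share leaving early, Rc the response rate in completers and Rl the rate in leavers. The all-treated rate is (1 − d)Rc + d·Rl, so

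evaluable rate − all-treated rate = d(Rc − Rl).

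The documents plan no value for d, so 5% and 10% are assumptions. Take Rc = 0.40.

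| d | Rl = 0 | Rl = 0.20 |
|---|---|---|
| 5% | 0.05 × 0.40 = 2.0 points | 0.05 × 0.20 = 1.0 point |
| 10% | 0.10 × 0.40 = 4.0 points | 0.10 × 0.20 = 2.0 points |

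At d = 0 the bias is zero.

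**4. False-go chance if 10% is read as the all-treated rate.** The completer rate is then q = (0.10 − d·Rl)/(1 − d).

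| d | Rl | q | at least 4 of 15 | at least 3 of 10 |
|---|---|---|---|---|
| 0 | – | 0.1000 | 5.6% | 7.0% |
| 5% | 0 | 0.10/0.95 = 0.1053 | 6.5% | 8.0% |
| 10% | 0 | 0.10/0.90 = 0.1111 | 7.6% | 9.1% |
| 5% | 5% | 0.0975/0.95 = 0.1026 | 6.0% | 7.5% |
| 10% | 5% | 0.0950/0.90 = 0.1056 | 6.6% | 8.0% |

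For scale, section 10.4 keeps the threshold at four responders when 16 to 18 HIV positive subjects are enrolled. At a true 10%, P(at least 4) is 6.8%, 8.3% and 9.8% for n = 16, 17 and 18.

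**5. What the report would show at the threshold.** Exact (Clopper-Pearson) 95% intervals, leavers counted as non-responders:

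| Cohort | Evaluable | All treated |
|---|---|---|
| HIV positive, two leavers | 4/15 = 26.7% (7.8 to 55.1) | 4/17 = 23.5% (6.8 to 49.9) |
| HIV negative, one leaver | 3/10 = 30.0% (6.7 to 65.2) | 3/11 = 27.3% (6.0 to 61.0) |

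**The case against.** The other side has real points, mostly about size.

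- **Progression seldom removes anyone early.** Under section 3.6.1.7 it ends therapy only if clinically significant and sustained for eight weeks, and Table 1 in section 3.3 holds drug for many toxicities. Most early progressors will finish two cycles and count as non-responders. This stands. Discontinuing toxicity, withdrawal and non-adherence remain.
- **Few inevaluable subjects are expected.** Section 10.3 says so, and section 3.1.5 reports that the first six patients finished 8 weeks without a DLT. This stands, but 0 of 6 has an exact 95% upper limit of about 46%, so it does not establish a low rate.
- **Two cycles is the least exposure at which response can be assessed, and the rule is prespecified.** True, and the stated probabilities are correct for the set they name. That supports keeping the evaluable analysis. It does not supply the rate in treated subjects.
- **The shift is small.** One to four points compares with stated interval half-widths of 26 and 32 points for the two cohorts, and the false-go shift is within what the plan accepts at 16 to 18 subjects. True, but interval width reflects chance, whereas this error tends in one direction.
- **Early leavers are visible elsewhere.** They remain in the safety assessment, and progression-free and event-free survival run from Day 1 with no stated two-cycle restriction. Neither shows their effect on the response rate.

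The second course offers only a soft contrast. Section 10.4 speaks of "The fraction of the patients who receive the extra course who respond to treatment", which points to everyone who receives it. But the rule in section 6.2 is general, and section 6.2.1.1 says second-course documentation follows the first-course scheme. The concern does not depend on that contrast.

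**Conclusion.** The concern holds as a reporting gap that should be fixed. As written, the plan yields a first-course response rate that exceeds the all-treated rate whenever leavers respond less often than completers, and nothing planned for the response endpoint would reveal by how much. Under the assumed 5% to 10% early dropout, with 40% response in completers, the excess is 1 to 4 points. The false-go chance, if 10% is taken as the all-treated rate, is 6.0% to 7.6% for 4 of 15 and 7.5% to 9.1% for 3 of 10. These figures rest on assumed dropout and assumed response in leavers; with no early leavers nothing changes. The go rules, the sample size and the stated operating characteristics are not invalidated.

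**What to change.** Keep the evaluable analysis and the go rules. Add to section 10.4:

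> For each cohort, and for the pooled rate if the cohorts are pooled, the first-course response rate with an exact 95% confidence interval will also be reported in all subjects who met the cohort's entry criteria and received at least one dose at the phase 2 dose. This includes qualifying subjects from the toxicity assessment phase and subjects later replaced. Subjects who stop before completing two cycles count as non-responders unless a response meeting section 6.2.3 is documented. This rate will be shown beside the evaluable rate, and each early leaver will be listed with the reason.

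Applying the entry criteria keeps out phase I HIV positive subjects who did not meet 2.1.1.15, a separate baseline restriction that serves its own purpose. Apply the same definitions to both cohorts, including the 15 HIV positive and 7 HIV negative subjects in the amendment G report. State that the 10% and 40% operating characteristics refer to evaluable subjects.

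The cost is one paragraph, one table and a short listing from data already collected. Sample size, power and go rules are unchanged. The added rate may come out slightly lower than the evaluable one. Because the HIV positive cohort was already accrued at amendment G, it should be labelled supplementary.

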3.1.5 Phase 2 (Expansion Cohort)

As of 06/28/2012, the first six patients completed the first 8 weeks of therapy without DLTs. Hence, the planned Phase I dose assessment phase has been completed, establishing that 5mg pomalidomide for 21 of 28 days is tolerable in this population. This is therefore the dose to be used for Phase II response assessment.

3.1.6 Option of Second Course of Pomalidomide (effective with Amendment D version date: 01/22/2013)

Following completion of the initial course of pomalidomide therapy (up to 48 weeks), subjects (from the Phase 1 or 2 portion of the study) who again manifest KS requiring therapy while not

taking pomalidomide within the study follow up period (5 years) may be considered for an additional course of therapy at the Phase 2 dose of 5mg 21 of 28 days, so long as each of the following criteria apply:

- 3.1.6.1 The subject achieved a tumor response (complete or partial) or derived other clinical benefit from their initial course of therapy (examples of clinical benefit being given in Section [3.1.4.2-3.1.4.4](#))
- 3.1.6.2 The KS present is progressing while not taking pomalidomide and either symptomatic (for example with pain, edema) or causing psychological distress)
- 3.1.6.3 The eligibility criteria described in Section [2.1](#) are again met at the time of consideration of an additional course of therapy, and no exclusion criteria are present except that item [2.1.2.12](#) (prior therapy with pomalidomide) will not apply. Screening evaluations described in Section [2.2](#). will be repeated at the time of consideration of an additional course of therapy.
- 3.1.6.4 Interval administration of other therapies for KS (local or systemic) will not preclude consideration of a second course of pomalidomide within the protocol, so long as the above criteria are met.
- 3.1.6.5 Drug administration, evaluations, and off-therapy criteria and correlative studies for the optional second course of therapy parallel those described for the initial course, except that pharmacokinetic studies and optional on-therapy research biopsies will not be performed for the second course. These evaluations are detailed in Section [3.4.2](#), “Optional Second Treatment Course Study Calendar”.

In the absence of off-therapy criteria, the second course of therapy will continue for 24 weeks (6 cycles of 4 weeks each). Subjects who, in the opinion of the investigators, are continuing to derive benefit may continue on the second course therapy for up to an additional 24 weeks (6 additional cycles). Thus the maximal duration of pomalidomide therapy that may be administered within the protocol is 96 weeks (two courses of 48 weeks each); though in most cases the amount administered will be considerably less.

